### **15.6.9 Sensitivity Analyses for the Primary Endpoint**

The robustness of the results of the principal analysis of the primary endpoint will be explored employing the following:

#### **15.6.9.1 Sensitivity Analysis Using Difference Analyses Sets**

The primary analysis described above will be used for the ITT, mITT, CO and PP Analysis Sets with or without efficacy measurements taken after study treatment termination.

#### **15.6.9.2 Sensitivity Analysis Using Change from Baseline to Last Observed Value (LOV)**

The Total UPDRS score change from baseline to last observed value (LOV), with or without UPDRS measurements taken after study treatment termination, will be calculated and analyzed for the ITT Analysis Set.

The statistical model to be used for the analysis of the change from baseline to LOV in the Total UPDRS score will be an analysis of covariance (SAS® MIXED procedure) and the model will include treatment group, CGR and baseline Total UPDRS score. The change from baseline to LOV will be used as response variable in the model and differences between P2B001 0.6/0.75mg to its 2 individual components at LOV will be tested using 2 contrasts: P2B001 0.6/0.75mg vs. pramipexole 0.6mg and P2B001 0.6/0.75mg vs. rasagiline 0.75mg.

#### **15.6.9.3 Sensitivity Analysis Using the Total UPDRS Responders Analysis**

The ITT analysis set will further be used to compare the LOV responders' rate, with or without UPDRS measurements taken after study treatment termination, between the P2B001 0.6/0.75mg and its 2 individual components in the primary endpoint.

A subject with an improvement of 4 point or more at LOVas compared to baseline will be classified as a “Responder” while other randomized subjects not falling into this definition will be classified as a “Non-Responders”.

The analysis of this binary end-point will be based on estimating 2 contrasts (2 contrasts: P2B001 0.6/0.75mg vs. pramipexole 0.6mg and P2B001 0.6/0.75mg vs. rasagiline 0.75mg) derived from a baseline-adjusted, Logistic Regression model [SAS® PROC GENMOD with DIST=BIN and LINK=LOGIT] to this binary outcome measure. In addition to the treatment group the model will include the following covariates: CGR and baseline Total UPDRS score. The treatment effect (odds-ratios) of P2B001 0.6/0.75mg vs its 2 individual components at LOV on the proportion of responders at week 12/Treatment Termination and the corresponding adjusted proportions will be displayed. In addition, the number and proportion of responders at Week 12/Treatment Termination will be displayed by treatment group.

#### **15.6.9.4 Sensitivity Analysis Accounting for Missing Values**

The ITT analysis set will be used for the below sensitivity analysis.

To evaluate the possible impact of missing values on the principal analysis of the primary endpoint results assuming all missing data are Missing Not At Random (MNAR), a sensitivity analysis using the **Tipping Point Method** and multiple imputations will be performed according to the following steps:

1. Multiple Imputations Assuming Missing At Random Missingness Mechanism: The Multiple Imputations procedure, using the Markov-Chain-Monte-Carlo (MCMC) method (SAS® MI procedure) will be used on the total UPDRS at baseline and at LOV, with or without UPDRS measurements taken after study treatment termination, to impute Missing At Random (MAR) missing values. Treatment and country will be included in the imputation model.  
The number of imputations that will be used will be 100. Minimum and maximum imputation values will be 0 and 160 in line with the total UPDRS score range. The seed that will be used for the MI procedure random numbers generator will be 12345678.
2. The change from baseline based on step 1 will then be calculated.
3. For the P2B001 0.6/0.75mg -treated subjects only with imputed missing values, the value of **S**, the tipping parameter, where  $S \geq 0$  (reduction over time is an improvement), will be added to the calculated change from baseline artificially worsening the change for these imputed values.
4. Each of the 100 imputed data sets for a given **S** will be analyzed using an ANCOVA model (SAS® MIXED procedure) to derive the treatment effect of the P2B001 0.6/0.75mg vs its 2 individual components and standard errors. The model will include treatment, country and baseline Total UPDRS score.
5. Treatment effects, 95% CIs and p-values will be calculated for a given **S** using the SAS® MIANALYZE procedure on the treatment effects and SE estimates for each of the 100 imputed datasets.

6. Imputations and analyses will be repeated while increasing **S** by 1% each time until one of the two p-values (for the two between groups contrasts) in the primary model will be greater than 0.05. The first **S** causing significance on both contrasts to be lost is the **tipping point**.

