#### **15.6.7 Efficacy Endpoints and Analyses**

All efficacy endpoints will be tested for the ITT analysis set controlling for multiplicity as detailed in Section 15.5.

An effort to obtain the efficacy outcome measures data regardless if study treatment was discontinued will be made.

Week 12/Treatment Termination is defined for all statistical analyses involving significance testing as the last visit in which a subject was treated with the study drug.

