#### **15.6.8 Primary Efficacy Endpoint and Principal Statistical Analysis**

The primary efficacy endpoint for this study is the change from baseline to Week 12/Treatment Termination in total UPDRS score (defined as sum of parts II and III, scores (0-160). The statistical

model will be a Mixed Model for Repeated Measures (MMRM) (SAS® MIXED procedure with REPEATED sub-command). The model will include the following fixed effects: categorical week in trial by treatment interaction, country or geographical region (CGR), and baseline UPDRS score. The model will use the unstructured covariance structure and the REML estimation method and degrees of freedom will be adjusted using the Kenward-Roger method. Data from all three changes from baseline to post-baseline visits (weeks 4, 8 and 12) collected from all subjects randomized into the study will be used as response in the model. The differences between the P2B001 0.6/0.75mg arm as compared to its 2 individual components at Week 12/Treatment Termination will be estimated and tested using 2 contrasts: P2B001 0.6/0.75mg vs. pramipexole 0.6mg and P2B001 0.6/0.75mg vs. rasagiline 0.75mg. The study primary endpoint will be considered as met only if both contrasts will favor P2B001 0.6/0.75mg at a two-tailed alpha level of 5% each.

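### In the protocol text, the tipping-point analysis imputes the last observed UPDRS, not the Week 12 score, so its S overstates the robustness of the Week 12 MMRM; step 6 is also internally inconsistent

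*Protocol*

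**What the plan says.** Protocol 15.6.8 makes the principal analysis an MMRM with week-by-treatment terms, and the two contrasts are tested at Week 12/Treatment Termination. The responses are by visit: "Data from all three changes from baseline to post-baseline visits (weeks 4, 8 and 12"), where the synopsis and Appendix I place the first of these visits at week 5.

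Protocol 15.6.9.4 states its aim as the "impact of missing values on the principal analysis of the primary endpoint results", with all missing data taken as missing not at random. Its steps are:

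- Step 1: multiple imputation "will be used on the total UPDRS at baseline and at LOV, with or without UPDRS measurements taken after study treatment termination". LOV is the last observed value.
- Step 3: for P2B001 subjects with imputed values only, S "will be added to the calculated change from baseline artificially worsening the change for these imputed values".
- Step 4: an ANCOVA on each imputed data set.
- Step 6: S is raised "by 1% each time until one of the two p-values" exceeds 0.05, yet the tipping point is the first S "causing significance on both contrasts to be lost is the" tipping point.

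Protocol 15.6.9.2 already has a separate LOV analysis: "The change from baseline to LOV will be used as response variable in the model". Protocol 15.6.7 defines Week 12/Treatment Termination, for significance testing, "as the last visit in which a subject was treated with the study drug".

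Protocol 15.13 gives the SAP precedence. Only the addendum to SAP v2.0 is supplied. It does not mention the tipping point. It shows that mITT is now the principal efficacy set, and it maps the termination-visit UPDRS of 13 early terminators to week 5.

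**The concern.** The stated target and the imputed variable differ. The MMRM relies on missing-at-random for every subject without a Week 12 score. A tipping-point analysis should penalise those same unobserved values and show how much worse they must be before the result is lost. Imputing LOV penalises a smaller group: mainly those with no usable post-baseline score at all. The fewer subjects who carry the penalty, the larger S must be before significance goes.

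This is the only analysis in the supplied text presented as a missing-not-at-random check. A large S could be reported as robustness to missing Week 12 data when most subjects lacking Week 12 were never penalised.

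**Working it through.** **Inputs (Protocol 15.1):** effects 2.25 points over pramipexole 0.6 mg and 3.0 over rasagiline; SD 6; correlations 0.7 and 0.49; 10% missing at random; 150 per arm; both contrasts at two-sided 5%.

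**Assumptions:** 10% of each arm lacks Week 12 (15 of 150); the effect at LOV equals that at Week 12; q is the share of those 15 with no LOV. The documents do not give q.

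**1. The plan's own figure.** Joint power of two contrasts sharing an arm (correlation 0.5), with SE = 6√(2/n_eff) and n_eff the MMRM information at Week 12:

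- independent 10% missing per visit: n_eff 141.6, power 87.8%;
- monotone dropout in equal thirds: 138.5, 87.1%;
- monotone, every dropout with an earlier score: 140.2, 87.5%.

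The stated 87.6% reproduces.

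**2. Who is shifted in the P2B001 arm.**

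| Subject | Run with post-treatment data | Run without |
|---|---|---|
| Baseline and on-treatment week 5 or 8 score, no Week 12 score | not shifted | not shifted |
| Same, but with an off-treatment Week 12 score | LOV is that score; nothing missing | earlier score kept; not shifted |
| Only post-baseline UPDRS taken after stopping treatment | not shifted | imputed, shifted |
| No post-baseline UPDRS | imputed, shifted | imputed, shifted |
| No baseline UPDRS | change rests on an imputed baseline | same |

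The first row (both runs) and the second row (run without) are the gap: the MMRM on the same data has no Week 12 response for these subjects.

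**3. Effect on S.** With f the shifted share of the P2B001 arm, a contrast of size d is lost when d − fS < 1.96·SE. Two SE variants:

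- A: SE = 6√(2/(150(1−f)))
- B: SE² = (36 + f(1−f)S²)/150 + 36/150 + 2·36·(f/(1−f))/150, solved for S

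For d = 2.25, the contrast lost first:

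| Case | f | S, variant A | S, variant B |
|---|---|---|---|
| Week 12 shifted | 0.10 | (2.25 − 1.96×0.7303)/0.10 = 8.2 | 7.7 |
| LOV, q = 1/2 | 0.05 | 17.1 | 15.2 |
| LOV, q = 1/3 | 0.0333 | (2.25 − 1.96×0.7047)/0.0333 = 26.1 | 22.0 |
| LOV, q = 1/5 | 0.02 | 43.9 | 34.0 |

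Using the MMRM information for the SE gives 8.4 to 8.5 for the Week 12 target and 25 for LOV at q = 1/3. A simulation (200 runs per cell, 20 imputations, S in steps of 1, medians over runs significant at S = 0) gives 8 to 10 for Week 12 and 17, 28 and 35 for LOV at q = 1/2, 1/3 and 1/5. Overall: about 8 to 10 against about 22 to 28 at q = 1/3.

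**4. The addendum's 13 subjects.** Pro rata by 2:2:2:1 (an assumption), 13 × 2/7 = 3.7, about 4 in P2B001. In the run without post-treatment data, if their termination scores count as post-treatment and nobody else lacks an LOV, f = 3.7/150 = 0.0248. Variant A gives (2.25 − 1.96×0.7016)/0.0248 ≈ 35, variant B about 28. In the run with such data they have an LOV and are not shifted.

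**5. Step 6.** At f = 0.10, losing one contrast needs S of about 8. Losing both (d = 3.0) needs (3.0 − 1.4314)/0.10 = 15.7 (A) or 14.2 (B), and about 16 with the MMRM information. A relative 1% step from S = 0 stays at 0. As an additive step it could be 1.6 points (1% of 160), 0.06 (1% of SD 6) or 0.0225 (1% of 2.25).

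**The case against.** **The governing text is unseen.** SAP v2.0 may have replaced this method; it already changed the principal analysis set. This stands, and it makes the point conditional.

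**LOV may be the intended endpoint.** Protocol 15.6.7 defines Week 12/Treatment Termination as the last treated visit, and 15.6.9.3 uses LOV and Week 12/Treatment Termination almost interchangeably. On that reading an early stopper's last on-treatment score is the endpoint, not a missing value. This shows a real ambiguity but does not rescue the analysis as described. The MMRM takes week-specific responses, 15.6.9.2 already covers LOV, and the addendum maps early-termination scores to week 5, leaving Week 12 missing for those subjects.

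**Other analyses and follow-up help.** Protocol 15.6.9.1 repeats the MMRM with and without post-treatment data in four sets. The responder analysis counts randomised subjects without a qualifying improvement as non-responders. Sections 9.2.11 and 9.2.11.1 ask stoppers to stay in follow-up and leavers to have a termination UPDRS. The follow-up narrows the gap in the run with post-treatment data. None of these stresses the MMRM's assumption about missing Week 12 values.

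**Stronger readings a reader might infer.**

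- That no early dropout is ever shifted. The last three rows of the table in the working show otherwise.
- That almost nobody would be imputed, because independent 10% missingness at three visits leaves 0.1³ of subjects without a score. That predicts 525 × 0.001 ≈ 0.5 subjects, whereas the addendum reports 13 dosed subjects with no scheduled post-baseline UPDRS.
- That on mITT nobody would be imputed in the run with post-treatment data. This needs SAP v2.0 both to keep LOV and to run the analysis on mITT; neither is established, and 15.6.9.4 specifies ITT.

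**Conclusion.** The point holds for the protocol text, conditional on SAP v2.0. As written, the analysis does not test what it says it tests, and S is biased upward, given a similar treatment effect at LOV and Week 12. At planning values S rises from about 8 to 10 points to about 22 to 28 if a third of subjects missing Week 12 lack an LOV, and to about 28 to 35 if only the pro rata share of the addendum's 13 is shifted. These figures illustrate scale; the actual dropout pattern is not in the documents.

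Step 6 contradicts itself: about 8 points on one reading against 14 to 16 on the other at 10% shifted. Only the either-contrast reading fits the loop, which stops there. The 1% step cannot be programmed without a guess.

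A reader might infer that the primary result is compromised. It is not: the primary test, type I error and power do not depend on this analysis. Severity is minor to should-fix.

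**What to change.** Check SAP v2.0 first; if it already imputes and shifts Week 12, and defines the step and stopping rule, nothing is needed. If it kept the protocol text:

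1. Impute total UPDRS at weeks 5, 8 and 12, with treatment, baseline and the primary model's region term (CGR) in the imputation model.
2. Add S to imputed Week 12 changes in the P2B001 arm, in both the run with and the run without post-treatment data.
3. State S in UPDRS points on a fixed grid starting at 0.
4. Define the tipping point as the first S at which either contrast has p > 0.05.
5. Report the number imputed per arm, and align the analysis set with the principal set now in force.

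If the last on-treatment value is the intended target, say so and do not present the analysis as a test of the Week 12 MMRM.

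The cost is wording and minor reprogramming. The reported tipping point will be smaller.

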#### **15.6.10 Key Secondary Efficacy Endpoints and Analyses**

All efficacy endpoints will be tested for the ITT analysis. Secondary endpoints will be tested once both primary endpoint contrasts (P2B001 0.6/0.75mg as compared to its individual components) will favor P2B001 0.6/0.75mg at a two-tailed alpha level of 5% each.

Multiplicity adjustment for multiple endpoints testing for the secondary endpoints will utilize the gate keeping hierarchical method according to the following order and plan:

##### **15.6.10.1 Change from Baseline to Week 12/Treatment Termination in the ESS**

For the 1st secondary endpoint, namely, the P2B001 0.6/0.75mg vs. Pramipexole ER contrast in the change from baseline to Week 12/Treatment Termination in the ESS, will be considered as met only if both primary endpoint contrasts as above defined and the P2B001 0.6/0.75mg vs. pramipexole ER contrast in the change from baseline to Week 12/Treatment Termination in the ESS will all be met (total of 3 contrasts) at a two-tailed alpha level of 5% each.

The statistical model to be used for the analysis of the change from baseline to Week 12/Treatment Termination in the ESS will be a Mixed Model for Repeated Measures (MMRM) (SAS® MIXED procedure with REPEATED sub-command). The model will include the following fixed effects: categorical week in trial by treatment interaction, CGR, and baseline ESS score. The model will use the unstructured covariance structure and the REML estimation method and degrees of freedom will be adjusted using the Kenward-Roger method. Data from all three changes from baseline to post-baseline visits (weeks 5, 8 and 12) collected from all subjects randomized into the study will be used as response in the model. The difference between the P2B001 0.6/0.75mg as compared to Pramipexole ER at Week 12/Treatment Termination will be estimated and tested using a contrast.

##### **15.6.10.2 Change from Baseline to Week 12/Treatment Termination in the Total PDQ39**

The 2nd secondary endpoint, namely, the change from baseline to Week 12/Treatment Termination visit in the Total PDQ39 will be considered as met if all of the 3 previous tested contrasts (primary endpoint and 1st secondary endpoint) as well the two contrasts: P2B001 0.6/0.75mg vs. pramipexole 0.6mg once daily and, P2B001 0.6/0.75mg vs. rasagiline 0.75mg once daily in the 2nd secondary endpoint will all be met (total of 5 contrasts) at a two-tailed alpha level of 5% each.

The statistical model to be used for the analysis of the change from baseline to Week 12/Treatment Termination visit in the Total PDQ39 will be an analysis of covariance (SAS® MIXED procedure) and the model will include treatment group, CGR and baseline PDQ39 score. The change from baseline to Week 12/Treatment Termination will be used as response variable in the model and differences between P2B001 0.6/0.75mg to its 2 individual components at Week 12/Treatment

Termination will be tested using 2 contrasts: P2B001 0.6/0.75mg vs. pramipexole 0.6mg and P2B001 0.6/0.75mg vs. rasagiline 0.75mg.

#### **15.6.10.3 Change from Baseline to Week 12/Treatment Termination in the ADL UPDRS (part II)**

The 3rd secondary endpoint, namely, the change from baseline to Week 12/Treatment Termination in the ADL UPDRS (part II) score will be considered as met if all of the 5 previous tested contrasts (primary endpoint, 1st and 2nd secondary endpoints) as well the two contrasts: P2B001 0.6/0.75mg vs. pramipexole 0.6mg once daily and, P2B001 0.6/0.75mg vs. rasagiline 0.75mg once daily in the 3rd secondary endpoint will all be met (total of 7 contrasts) at a two-tailed alpha level of 5% each. The statistical model to be used for the analysis of the change from baseline to Week 12/Treatment Termination in the ADL UPDRS (part II) will be a Mixed Model for Repeated Measures (MMRM) (SAS® MIXED procedure with REPEATED sub-command). The model will include the following fixed effects: categorical week in trial by treatment interaction, CGR, and baseline ADL UPDRS (part II). The model will use the unstructured covariance structure and the REML estimation method and degrees of freedom will be adjusted using the Kenward-Roger method. Data from all three changes from baseline to post-baseline visits (weeks 5, 8 and 12) collected from all subjects randomized into the study will be used as response in the model.

The difference between P2B001 0.6/0.75mg to its 2 individual components at Week 12/Treatment Termination will be tested using 2 contrasts: P2B001 0.6/0.75mg vs. pramipexole 0.6mg and P2B001 0.6/0.75mg vs. rasagiline 0.75mg.

#### **15.6.10.4 Change from Baseline to Week 12/Treatment Termination in the Motor UPDRS (part III) Score**

The 4th secondary endpoint, namely, the change from baseline to Week 12/Treatment Termination in the motor UPDRS (part III) score will be considered as met if all of the 7 previous tested contrasts (primary endpoint, 1st, 2nd and 3rd secondary endpoints) as well the two contrasts: P2B001 0.6/0.75mg vs. pramipexole 0.6mg once daily and, P2B001 0.6/0.75mg vs. rasagiline 0.75mg once daily in the 4th secondary endpoint will all be met (total of 9 contrasts) at a two-tailed alpha level of 5% each.

The statistical model to be used for the analysis of the change from baseline to Week 12/Treatment Termination in the Motor UPDRS (part III) will be a Mixed Model for Repeated Measures (MMRM) (SAS® MIXED procedure with REPEATED sub-command). The model will include the following fixed effects: categorical week in trial by treatment interaction, CGR, and baseline Motor UPDRS (part III). The model will use the unstructured covariance structure and the REML estimation method and degrees of freedom will be adjusted using the Kenward-Roger method. Data from all three changes from baseline to post-baseline visits (weeks 5, 8 and 12) collected from all subjects randomized into the study will be used as response in the model.

The difference between P2B001 0.6/0.75mg to its 2 individual components at Week 12/Treatment Termination will be tested using 2 contrasts: P2B001 0.6/0.75mg vs. pramipexole 0.6mg and P2B001 0.6/0.75mg vs. rasagiline 0.75mg.

**15.6.10.5 CGI-S Responder's Analysis at Week 12/Treatment Termination (change from baseline  $\geq 1$  CGI-S points)**

The 5th secondary endpoint, namely, the CGI-S responder's analysis at Week 12/Treatment Termination (change from baseline  $\geq 1$  CGI-S points) will be considered as met if all of the 9 previous tested contrasts (primary endpoint, 1st, 2nd, 3rd and 4th secondary endpoints) as well the two contrasts: P2B001 0.6/0.75mg vs. pramipexole 0.6mg once daily and, P2B001 0.6/0.75mg vs. rasagiline 0.75mg once daily in the 4th secondary endpoint will all be met (total of 11 contrasts) at a two-tailed alpha level of 5% each.

A subject with an improvement of 1 point or more at Week 12/Treatment Termination as compared to baseline will be classified as a "Responder" while other randomized subjects not falling into this definition will be classified as a "Non-Responders".

The analysis of this binary end-point will be based on estimating 2 contrasts (2 contrasts: P2B001 0.6/0.75mg vs. pramipexole 0.6mg and P2B001 0.6/0.75mg vs. rasagiline 0.75mg) derived from a baseline-adjusted, Logistic Regression model [SAS® PROC GENMOD with DIST=BIN and LINK=LOGIT] to this binary outcome measure. In addition to the treatment group the model will include the following covariates: CGR and baseline CGI-S. The treatment effect (odds-ratios) of P2B001 0.6/0.75mg vs its 2 individual components at Week 12/Treatment Termination on the proportion of responders at Week 12/Treatment Termination and the corresponding adjusted proportions will be displayed. In addition, the number and proportion of responders at Week 12/Treatment Termination will be displayed by treatment group. Exploratory Efficacy Endpoints

Analyses of the exploratory endpoints will provide additional insight into the therapeutic effect of P2B001 0.6/0.75. These endpoints will be tested for the ITT analysis set using the nominal alpha level of 5% without controlling for multiplicity. Detailed statistical methodology to be used for the analyses of these exploratory endpoints will be provided in a more detailed SAP to be developed while the study is ongoing and prior to locking the database and unblinding.

